### 7.1.3. Analysis Methods

In general, the AEs following vaccination will be summarized (ie, tables of descriptive statistics) by vaccination schedule and presented per period/phase. The presentation will be according to the cohorts as shown in

[Table 4](#). Similar summary tables will also be provided pooled by vaccine (dose).

Furthermore, unsolicited AEs will be summarized (showing number and percentage) by System Organ Class (SOC) and Preferred Term (PT). Solicited AEs (recorded by day) will be converted into the analysis format of unsolicited AEs (recorded by event), as detailed in Attachment 2. These solicited AEs will be summarized by class (local, systemic) and Preferred Term. For solicited as well as unsolicited AEs, tables focusing on severity will be created. Focus will also be on the relationship (to the study vaccine) of the solicited systemic and unsolicited AEs.

The SAEs, AEs with fatal outcome, AEs leading to permanent discontinuation from boost vaccine administration, Grade 3 AEs and IREs will also be listed. A table summarizing all those parameters will further be created and presented per analysis period and vaccination schedule. Summary tabulations by SOC and PT for each of the category of events (ie, SAEs, AEs with fatal outcome, AEs leading to permanent discontinuation from boost vaccination, Grade 3 AEs and immediate reportable events) will also be generated on the entire reporting period and presented by vaccination schedule. Subject narratives will be generated for these events, except Grade 3 AEs. For Grade 3 AEs, the narratives will only be generated for those AEs that are considered related to study vaccination.

For the most frequent (at least 10% of subjects in any vaccination schedule) solicited local and systemic AEs, the duration and time to first onset of the events will also be summarized. If a subject experiences more than 1 occurrence of a solicited event, the maximum duration of the events will be used. The time to first onset is defined as:

$$[\textit{date of first onset} - \textit{reference date} + 1]$$

The reference date is the start date of each vaccination period (ie, Post-dose 1 or Post-dose 2). Duration and time to onset of AEs will be expressed in days.

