The study consists of a screening phase of up to 12 weeks (starting from the moment the subject signs the informed consent form [ICF]), a vaccination phase in which subjects will be vaccinated at baseline (Day 1), followed by a boost vaccination on Days 29, 57 or 85, and a post-vaccination phase and long-term follow-up phase until Day 365 (or until the start of the roll-over study or for an additional 12 months [whichever comes first] for subjects in France who agree to continue the long-term follow-up after Day 365, see details below). After unblinding, the subjects who received placebo in Cohorts II and III will be contacted by the site to communicate that they have completed the study and no further follow-up is required. Unblinding will be done when the last subject in the study completes the 6-month post-boost visit or discontinues earlier and the clinical database is locked. However, subjects who received placebo and reach the Day 365 visit prior to unblinding will be required to attend the Day 365 visit. After unblinding, only subjects who received Ad26.ZEBOV or MVA-BN-Filo will continue the study until the Day 365 (or until the start of the roll-over study or for an additional 12 months [whichever comes first] for subjects in France who agree to continue the long-term follow-up after Day 365, see details below) visit to assess long-term safety and immunogenicity.

An Independent Data Monitoring Committee (IDMC) will be commissioned for this study.

The sponsor halted all vaccinations in this study due to the occurrence of a serious and very rare condition, Miller Fisher syndrome, reported in the current study VAC52150EBL2001, until a revised ICF containing updated safety language was prepared and approval to restart the study was granted by the relevant competent authority. The study pause interrupted dosing of subjects, some awaiting prime vaccination and some awaiting boost vaccination. When approval was granted in the UK to restart the

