study under Amendment 4, the sponsor offered a late boost vaccination to those subjects who did not receive it yet, unless participants had withdrawn from the trial or were not eligible to receive the boost. Vaccinated subjects have been following the same post-boost vaccination schedule as those subjects unaffected by the pause. Subjects who did not receive the late boost were encouraged to return for the 1-year post-prime visit. After restart of the study in the UK under Amendment 4, screening for Groups 1 and 2 restarted, but randomization to Group 3 was stopped to focus on the schedules for which an indication will be sought. After approval of Amendment 5, enrollment in the entire study will be stopped.

Subjects in the UK and France who reach the Day 365 visit prior to unblinding will be approached to consent for enrollment into the VAC52150 Vaccine Development Roll-over study (VAC52150EBL4001) for long-term surveillance (for a total of up to 60 months after the prime vaccination). After unblinding, only subjects who received Ad26.ZEBOV and/or MVA-BN-Filo will remain in the VAC52150 Vaccine Development Roll-over study for long-term surveillance. After unblinding, subjects who received placebo and have already been enrolled into the VAC52150 Vaccine Development Roll-over study will be discontinued from further participation in the roll-over study. The parent(s)/legal guardian of children born to vaccinated female subjects who became pregnant with estimated conception within 28 days after vaccination with MVA-BN-Filo or within 3 months after vaccination with Ad26.ZEBOV, will also be approached to consent for enrollment of their offspring into the roll-over study, according to the same rules that apply for the other subjects. Subjects in France who agree to continue the long-term follow-up after Day 365 and reach the Day 365 visit before the roll-over study is opened, will have further follow-ups in the current study until they have started in the roll-over study or for an additional 12 months (whichever comes first) or discontinued earlier. These subjects will be contacted by telephone every 3 months after Day 365 (subjects will only visit the site when clinically indicated) for the collection of information on adverse events, serious adverse events, and immediate reportable events (IREs) that were ongoing at the Day 365 visit, and to report and follow up on new serious adverse events, pregnancies, and IREs.

SUBJECT POPULATION

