9.2. Safety Evaluations

9.2.1. Safety Endpoints

Primary Endpoints:

- Adverse events, collected from signing of the ICF onwards until the 42-day post-boost visit (Day 71 in Group 1; Day 99 in Group 2; and Day 127 in Group 3).
- Serious adverse events and IREs, collected from signing of the ICF onwards until the end of the study.
- Solicited local and systemic adverse events (reactogenicity) until 7 days after each study vaccine administration.

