11.4. Safety Analyses

No formal statistical testing of safety data is planned. Safety data will be analyzed descriptively (including 95% confidence intervals, if applicable), by cohort and overall.

Baseline for all safety parameters will be defined as the last value before the prime vaccination.

Adverse Events (Including Reactogenicity)

The verbatim terms used in the CRF by investigators to report adverse events will be coded using the Medical Dictionary for Regulatory Activities (MedDRA). All reported adverse events (solicited local, solicited systemic, and unsolicited) will be included in the analysis. For each

adverse event, the number and percentage of subjects who experience at least 1 occurrence of the given event will be summarized by group. Summaries, listings, datasets, or subject narratives may be provided, as appropriate, for those subjects who die, who discontinue study vaccine due to an adverse event, or who experience a severe or a serious adverse event.

The analysis for solicited adverse events will be done on those subjects in the Full Analysis set for whom reactogenicity assessments are available in the database. The analysis of unsolicited adverse events will be done on the Full Analysis set.

Clinical Laboratory Tests

Laboratory abnormalities will be determined according to the toxicity grading tables, and in accordance with the normal ranges of the clinical laboratory. The most severe laboratory abnormalities following vaccination will be tabulated per regimen.

Vital Signs and Electrocardiogram

Vital signs and ECG abnormalities following vaccination will be tabulated by most severe abnormality grade.

Physical Examination

Physical examination abnormalities following vaccination will be tabulated by most severe abnormality grade.

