## 7. SAFETY

The safety and tolerability data include the following:

- AEs collected from signing of the informed consent form (ICF) onwards until the 42-day post-boost visit.
- Serious adverse events (SAEs) and immediate reportable events (IREs) from signing of the ICF onwards until the end of the study.
- Solicited local and systemic AEs (reactogenicity) recorded during the first 8 days (including the day of the vaccination) following each vaccination.

The safety and tolerability data will be summarized based on the full analysis set. The analysis will be based on the actual dose (ie, Dose 1 and Dose 2 for the prime and boost vaccinations, respectively) that the subjects received. For example, if Dose 2 is not administered to a subject, then that subject will not be included in the analysis of AEs in the Post-dose 2 period. Focus will be on safety signals detected during the Post-dose 1 and Post-dose 2 periods, as well as the Regimen phase.

- The safety data will be evaluated based on the pooled (matching on vaccination schedules) cohorts II and III. The data will be presented separately for Cohort I and Group 4. See

[Table 4](#) for an overview.

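### Full-period SAE and IRE percentages rest on follow-up that can differ by arm after unblinding, and nothing planned would show whether it did

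*SAP*

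**What the plan says.** **Collection.** SAEs and IREs are primary endpoints. Protocol 9.2.1 has "Serious adverse events and IREs, collected from signing of the ICF onwards until the end of the study"; SAP Section 7 repeats it: "Serious adverse events (SAEs) and immediate reportable events (IREs) from signing of the ICF onwards until the end of the study". The length of the window therefore depends on how long each subject is followed.

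**Tabulation.** SAP 7.1.3 says the SOC and PT tables for these categories "will also be generated on the entire reporting period and presented by vaccination schedule". Protocol 11.4 gives the statistic: "the number and percentage of subjects who experience at least 1 occurrence of the given event will be summarized by group". Neither document plans a person-time rate, a cut-off common to both arms for the full period, or a summary of follow-up time by arm. SAP 5.1 (disposition) gives counts, percentages and reasons only.

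**Follow-up by arm.** In the Protocol Synopsis (Overview of Study Design), once the study is unblinded, "the subjects who received placebo in Cohorts II and III will be contacted by the site to communicate that they have completed the study". For the other arm: "After unblinding, only subjects who received Ad26.ZEBOV or MVA-BN-Filo will continue the study until the Day 365" visit. French subjects who agree, and who reach Day 365 before the roll-over study opens, "will have further follow-ups in the current study until they have started in the roll-over study or for an additional 12 months". There is a limit: "However, subjects who received placebo and reach the Day 365 visit prior to unblinding will be required to attend the Day 365 visit". Protocol 10.1 also defines completion by arm: the 6-month post-boost visit for boosted placebo subjects, Day 365 for unboosted placebo subjects, and Day 365 for active subjects.

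**The concern.** Protocol 3.2 says the placebo group is there to show how often clinical changes occur without vaccine. If active subjects are observed longer, equal event rates give a higher active percentage, and the error can only run in that direction. The additional active time is also open-label. The IRE list includes isolated paresthesia, and Protocol 12.1.1 asks for suspected events to be reported before the diagnosis is settled, so reporting could respond to known allocation. Vaccination was halted over a Miller Fisher case, which is an IRE, so the IRE table will be read closely. Placebo numbers are small: 30 per group were originally planned (Protocol Table 2). A few late events seen only in the active arm could change how the table reads.

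**Working it through.** **1. Visit days.** Unblinding needs the last subject's 6-month post-boost visit (or earlier discontinuation) plus database lock. Boost day + 180 gives 29 + 180 = 209, 57 + 180 = 237 and 85 + 180 = 265. These match Protocol 9.1.5.

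**2. Per-subject upper bound to Day 365.** Take the last-primed placebo subject, released at the nominal visit day with no lock delay, against an active subject followed to Day 365. At an equal, constant, low hazard the ratio of crude percentages is close to the ratio of days. The check uses 1 − exp(−rate × days/365) at an assumed 2% per year, for which the active value is 1.98%.

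| Group | Days ratio | Placebo % | Ratio of percentages |
|---|---|---|---|
| 1 | 365/209 = 1.75 | 1.14 | 1.74 |
| 2 | 365/237 = 1.54 | 1.29 | 1.53 |
| 3 | 365/265 = 1.38 | 1.44 | 1.37 |

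Assumed rates of 1% to 5% per year barely change these.

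**3. Arm average to Day 365.** A placebo subject primed u days before the last-primed subject is followed for min(365, u + V + L) days, where V is the trigger visit day and L the lock delay. Subjects primed at least 365 − 209 = 156 days earlier (V = 209) or 365 − 237 = 128 days earlier (V = 237) lose nothing. With u assumed uniform on 0 to E and L = 0, the share cut short is (365 − V)/E and the mean loss is (365 − V)²/(2E). The documents do not give E. The 755 days used here run from the original protocol (27 March 2015) to Amendment 5 (20 April 2017).

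| V | E | Share cut short | Mean placebo days | Ratio |
|---|---|---|---|---|
| 209 | 365 | 43% | 365 − 33.3 = 331.7 | 1.10 |
| 237 | 365 | 35% | 365 − 22.4 = 342.6 | 1.07 |
| 209 | 755 | 21% | 365 − 16.1 = 348.9 | 1.05 |
| 237 | 755 | 17% | 365 − 10.9 = 354.1 | 1.03 |

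Sensitivity at V = 209:
- A shorter entry span raises the ratio: E = 180 gives 1.23.
- Lock delay lowers it: at E = 365, L = 30 gives 1.06 and L = 60 gives 1.04.
- L of 156 days or more gives 1.00.

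**4. French extension.** If a share q of active subjects complete the full extra 12 months and no placebo subject does, against placebo followed to Day 365, the mean follow-up ratio is (365 + 365q)/365 = 1 + q. That is 1.10 at q = 10% and 1.50 at q = 50%. Placebo subjects who enter while still blinded move it back towards 1.00.

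**5. Which events.** The mechanism applies to SAEs, fatal AEs and IREs. Non-serious Grade 3 AEs are collected only to 42 days post-boost, under one rule for both arms. Cohort I has no placebo. Group 4 is unblinded after its own 28-day visit, and its later follow-up rules are in a country-specific protocol that was not supplied.

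**The case against.** The strongest reply is that the gap may be nil.

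- **The protocol's rules narrow it.** Unblinding waits for the last subject in the whole study and for database lock. Placebo subjects who reach Day 365 first must attend it, and unboosted placebo subjects complete at Day 365 anyway. Late-boosted subjects have visits counted from the actual boost, so a boost on Day 185 or later puts the 6-month visit at or beyond Day 365 (185 + 180 = 365), which delays unblinding.
- **The dates point to late unblinding.** SAP Section 1 says the 6-month primary analysis was not performed. Amendment 5, dated 20 April 2017, says enrollment will not resume. If nobody was primed after that date, the last subject reached Day 365 by about 20 April 2018. SAP version 2.0, dated 30 May 2018, still places database lock in the future (Section 5.2).
- **Other outputs help.** SAP 7.1.3 also tabulates these events per analysis period. The post-dose periods end by relative Day 29 in both arms and are the SAP's stated focus. Events are listed individually with narratives, and no formal comparison is planned.

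Most of this stands, and it rules out saying that the tables do inflate the active arm. It does not close the point. SAP 1.5 describes unblinding after the 6-month visit and lock in the past tense, so the documents do not settle the date. The per-period table is like for like only within 28 days of each dose. The Post-dose 2 follow-up phase ends at last contact (SAP Table 2), so it has the same arm-dependent length. The Miller Fisher case arose about a month after boost, near that boundary. Descriptive percentages on unequal exposure mislead with or without a test.

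**Conclusion.** The point holds as a possible bias in one direction, of unknown and probably modest size. With equal true hazards, full-period crude percentages give an active/placebo ratio of 1.00 if unblinding follows all follow-up, and about 1.03 to 1.10 on average to Day 365 under the uniform-entry assumption (E of 365 to 755 days, trigger Day 209 or 237, no lock delay). Any one-sided French extension comes on top. This assumes that the tables show placebo beside active, that hazard is constant, and that visits fall on nominal days.

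A reader might infer more, and the documents do not support it:

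- **That the active arm is inflated by 1.75, 1.54 or 1.38.** These are upper bounds for a single last-primed placebo subject, not arm averages. The Group 3 value is the least likely to arise, because randomization to Group 3 was not resumed while screening for Groups 1 and 2 restarted in the UK.
- **That the ratio could be 3.5.** The figure 730/209 = 3.49 pairs the last-primed Group 1 placebo subject with a French active subject who completes the whole extension. It is not an arm-level ratio.
- **That the French extension is for active subjects only.** Entry does not depend on vaccine received; the restriction applies only after unblinding.

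The reason to act is that the planned outputs would not let a reader tell a ratio of 1.00 from one well above it, for a primary safety endpoint.

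**What to change.** In SAP 7.1.3, keep the full-period table and add the following:

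1. The unblinding date, and a summary of follow-up time by arm and schedule.
2. SAE and IRE incidence per person-year of actual follow-up.
3. A table by arm and schedule cut at unblinding for both arms. It should have no Day 365 cap, because a cap would remove post-boost time from late-boosted subjects. Events before Dose 1 stay in the listings.
4. Events after unblinding, shown separately as open-label follow-up.

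Items 2 and 3 belong together. A person-year rate assumes a constant hazard: if events cluster soon after vaccination, longer active follow-up would dilute the active rate. Nor does it deal with open-label reporting. The table cut at unblinding handles both.

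The cost is a few extra tables or columns, using last-contact dates that already define the periods in SAP Table 2. No new data are needed. Keeping the full-period table means that late events in vaccinated subjects remain visible.

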## 7.2. Clinical Laboratory Tests

This section concerns the clinical laboratory test data. The analysis of the laboratory assessments will be based on the Food and Drug Administration (FDA)'s Toxicity Grading Scale for Healthy Adult and Adolescent Volunteers Enrolled in Preventive Vaccine Clinical Trials (Attachments 3). In case no toxicity grades are defined for a test, the abnormalities above or below the normal range will be used.

It is important to note that any abnormal laboratory value that represents a clinically relevant increase in toxicity grade post study vaccination is also recorded on the AE page of the eCRF and will be analyzed as AEs.

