- arthralgia
- chills

If a *solicited local or systemic adverse event* is not resolved on Day 8, the follow-up will be captured in the diary. The subject will be instructed to record the date of last symptoms and maximum severity in the diary after resolution.

Cardiac Events

In case any cardiac sign or symptom develops after the boost vaccination, an ECG and troponin I test should be obtained and the subject should be referred to a local cardiologist.

Clinical Laboratory Tests

Blood samples for serum chemistry and hematology and for troponin I, serology and pregnancy testing (~15 mL) and a urine sample for urinalysis (dipstick) will be collected at screening. Blood samples for serum chemistry and hematology (~7 mL) will also be taken at additional time points as indicated in the [Time and Events Schedule](#). Samples can be taken in fasting or non-fasting conditions but should be documented in the CRF. The investigator must review the laboratory results, document this review and record any clinically relevant changes occurring during the study in the Adverse Event section of the CRF up to the 42-day post-boost visit. Thereafter, only serious adverse events need to be recorded. The laboratory reports must be filed with the source documents. For reporting of IREs, refer to Section [12.3.3](#).

The following tests will be performed by the central laboratory. Parameters marked with an asterisk (*) will only be measured at screening:

- Hematology and Coagulation Panel
 - hemoglobin
 - white blood cell (WBC) count with differential
 - platelet count
 - fibrinogen*
 - prothrombin time
 - activated partial thromboplastin time

Blood smear: A WBC evaluation may include any abnormal cells, which will then be reported by the laboratory. A hematology evaluation may include abnormalities in the red blood cell (RBC) count and/or RBC parameters and/or RBC morphology, which will then be reported by the laboratory. In addition, any other abnormal cells in a blood smear will also be reported. Only clinically significant abnormal WBC, abnormal RBC, or any other abnormal cells in a blood smear will be reported as adverse events.

- Serum Chemistry Panel
 - sodium
 - potassium
 - blood urea nitrogen (BUN)
 - aspartate aminotransferase (AST)
 - alanine aminotransferase (ALT)
 - glucose (fasting or non-fasting)*
 - albumin*
 - total protein*
 - total bilirubin*
 - creatinine
 - FSH*

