 - (only in women >45 years of age with amenorrhea <2 years or ≤45 years of age with amenorrhea >6 months)
- Urinalysis – Dipstick for:
 - glucose*
 - ketones*
 - protein*
 - blood*

In case of positive urinalysis dipstick results, the sediment will be examined microscopically (only RBC will be documented).

Additional clinical laboratory assessments to be performed by the central laboratory (unless otherwise specified) are as follows:

- Serum pregnancy test for women of childbearing potential at screening;
- Urine pregnancy test for women of childbearing potential before each study vaccination (by the **local** laboratory);
- Serology (HIV type 1 and type 2 antibody, HBsAg, and HCV antibody) at screening;
- Troponin I testing at screening.

Laboratory values will be determined according to the toxicity grading tables in [Attachment 1](#) if applicable for laboratory tests.

Any clinically significant abnormalities occurring from signing of the ICF onwards until 42 days after the boost vaccination must be recorded on the Adverse Event section of the CRF. Thereafter, reporting will be limited to all serious adverse events. All events should be followed (by repeat testing) to resolution, or until reaching a clinically stable endpoint. For reporting of IREs, refer to Section [12.3.3](#).

Electrocardiogram

A single, 12-lead ECG will be performed at the time points indicated in the [Time and Events Schedule](#) and interpreted locally. Additional ECG monitoring may be done at other time points during the study if clinically indicated based on signs and symptoms.

During the collection of ECGs, subjects should be in a quiet setting without distractions (eg, television, cell phones). Subjects should rest in a supine position for at least 5 minutes before ECG collection and should refrain from talking or moving arms or legs. If blood sampling or vital sign measurement is scheduled for the same time point as ECG recording, the procedures should be performed in the following order: vital signs, ECG(s), blood draw.

Any clinically significant abnormalities occurring from signing of the ICF onwards until 42 days after the boost vaccination must be recorded on the Adverse Event section of the CRF. Thereafter, reporting will be limited to all serious adverse events. All events should be followed to resolution, or until reaching a clinically stable endpoint. For reporting of IREs, refer to Section [12.3.3](#).

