	HI	144-145	146-147	≥148
Potassium (mEq/L or mmol/L)	LO	3.5-3.6	3.3-3.4	≤3.2
	HI	5.1-5.2	5.3-5.4	≥5.5
Glucose (mg/dL)	LO	65-69	55-64	≤54
	HI ^d	100-110	111-125	>125
	HI ^e	110-125	126-200	>200
Blood urea nitrogen	HI	23-26 (mg/dL) or 8.3-9.4 (mmol/L)	27-31 (mg/dL) or 9.5- 11.2 (mmol/L)	>31 (mg/dL) or >11.2 (mmol/L)
Creatinine	N	1.5-1.7 (mg/dL) or 133-151 (μmol/L)	1.8-2.0 (mg/dL) or 152-177 (μmol/L)	>2.0 (mg/dL) or >177 (μmol/L)
Calcium (mg/dL)	LO	8.0-8.4	7.5-7.9	<7.5
	HI	10.5-11.0	11.1-11.5	>11.5
Magnesium (mg/dL)	LO	1.3-1.5	1.1-1.2	<1.1
Phosphorus (mg/dL)	LO	2.3-2.5	2.0-2.2	<2.0
Creatine kinase (CK) (mg/dL)	N	1.25-1.5xULN	1.6-3.0xULN	≥3.1xULN
Albumin (g/dL)	LO	2.8-3.1	2.5-2.7	<2.5
Total protein (g/dL)	LO	5.5-6.0	5.0-5.4	<5.0
Alkaline phosphatase (U/L)	N	1.1-2xULN	2.1-3xULN	>3xULN
AST (U/L)	HI	1.1-2.5xULN	2.6-5xULN	>5xULN
ALT (U/L)	HI	1.1-2.5xULN	2.6-5xULN	>5xULN
Bilirubin, serum total (mg/dL) – when accompanied by any increase in Liver Function Test		1.1-1.25xULN	1.26-1.5xULN	>1.5xULN
Bilirubin, serum total (mg/dL) – when Liver Function Test is normal		1.1-1.5xULN	1.6-2.0xULN	>2.0xULN
Amylase (U/L)	N	1.1x1.5ULN	1.6-2.0xULN	>2.0xULN
Lipase (U/L)	N	1.1x1.5ULN	1.6-2.0xULN	>2.0xULN

^a Depending upon the laboratory used, references ranges, eligibility ranges and grading may be split out by sex and/or age.

^b Cardiac troponin I increase by factor: >ULN-<2.0xULN; ≥2.0-<5.0xULN; ≥5.0xULN. (This footnote is added by the sponsor).

^c Low, High, Not Graded.

^d Fasting.

^e Non-fasting.

Hematology	LO/HI/N^a	Mild (Grade 1)	Moderate (Grade 2)	Severe (Grade 3)
Hemoglobin (women) change from baseline (g/dL)	LO	Any decrease-1.5	1.6-2.0	>2.0
Hemoglobin (men) change from baseline (g/dL)	LO	Any decrease-1.5	1.6-2.0	>2.0
White blood cell count (cell/mm ³)	HI	10,800-15,000	15,001-20,000	>20,000
	LO	2,500-3,500	1,500-2,499	<1,500
Lymphocytes (cell/mm ³)	LO	750-1,000	500-749	< 500
Neutrophils (cell/mm ³)	LO	1,500-2,000	1,000-1,499	< 1000
Eosinophils (cell/mm ³)	HI	650-1500	1501-5000	> 5000
Platelets (cell/mm ³)	LO	125,000-140,000	100,000-124,000	<100,000
Coagulation				
Prothrombin time (PT, seconds)	HI	1.0-1.10xULN	1.11-1.20xULN	>1.20xULN
International normalized ratio (INR) ^b	HI	1.1-1.5xULN	1.6-2.0xULN	>2.0xULN
Partial thromboplastin time (PTT or aPTT, seconds)	HI	1.0-1.2xULN	1.21-1.4xULN	>1.4xULN
Fibrinogen (mg/dL)	HI	400-500	501-600	>600
	LO	150-200	125-149	<125
Urine				
Protein (dipstick)	HI	Trace	1+	2+
Glucose (dipstick)	HI	Trace	1+	2+

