### RANGES TO CONVERT FDA SCALE (mg/dL) TO SI UNITS

Blood, Serum, or Plasma Chemistries a	LO/HI/N b	Mild (Grade 1)	Moderate (Grade 2)	Severe (Grade 3)
Glucose (mmol/L)	LO	3.61-3.38	3.05-3.60	≤3.04
	HI c	5.55-6.11	6.12-6.94	>6.94
	HI d	6.11-6.94	6.95-11.10	>11.10
Blood urea nitrogen (mmol/L)	HI	8.2-9.3	9.4-11.1	>11.1
Creatinine (μmol/L)	HI	133-150	151-177	>177
Calcium (mmol/L)	LO	2.00-2.10	1.87-1.99	<1.87
	HI	2.62-2.74	2.75-2.87	>2.87
Magnesium (mmol/L)	LO	0.53-0.62	0.45-0.52	<0.45
Phosphorus (mmol/L)	LO	0.74-0.81	0.65-0.73	<0.65
Cholesterol (mmol/L)	HI	5.20-5.43	5.44-5.82	>5.82
Coagulation				
Fibrinogen (μmol/L)	HI	11.76-14.70	14.71-17.65	>17.65
	LO	4.41-5.88	3.68-4.40	<3.68

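### SAP Attachment 3 drops the protocol's three troponin I steps without declaring it, so a large post-boost rise can only be classed as above normal; BUN and creatinine SI cut-offs also differ slightly

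*SAP*

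**What the plan says.** **Protocol.** Section 9.2.2 refers to Attachment 1 for grading ("Laboratory values will be determined according to the toxicity grading tables in" that attachment), and Section 11.4 repeats the principle: "Laboratory abnormalities will be determined according to the toxicity grading tables". A footnote to the chemistry table in Attachment 1, marked as the sponsor's own addition, reads "Cardiac troponin I increase by factor: >ULN-<2.0xULN; ≥2.0-<5.0xULN; ≥5.0xULN". Troponin I is scheduled at screening only. Under Cardiac Events, Section 9.2.2 adds an unscheduled test: "In case any cardiac sign or symptom develops after the boost vaccination, an ECG and troponin I test should be obtained". Section 1.2.4 lists myo/pericarditis among the potential risks.

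**SAP.** Sections 7.2 and 7.2.3 grade laboratory results by SAP Attachment 3. For tests without a grade, 7.2 says: "In case no toxicity grades are defined for a test, the abnormalities above or below the normal range will be used". Section 7.2.1 takes the worst grade or abnormality over all post-baseline measurements in a period. It counts an abnormality as following vaccination only if it is worse than baseline, if it moves from low to high or the reverse, or if baseline is missing. Section 7.2.3 tabulates worst abnormalities with particular attention to Grade 3. Attachment 3 keeps the protocol's footnote on laboratory-specific reference ranges but has no troponin row or footnote. Section 3 lists only changes to the immunogenicity and per protocol analysis sets.

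**BUN and creatinine.** The mg/dL bounds are the same in both documents. The SI bounds are not. For example, BUN Grade 1 in the protocol is "23-26 (mg/dL) or 8.3-9.4 (mmol/L"), whereas the SAP's SI conversion table starts it at 8.2 and ends it at 9.3.

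**The concern.** Both attachments present themselves as the same three-grade scale, so a reader would expect one result to receive one grade. The troponin omission matters most. After the boost the test is done only when a cardiac sign or symptom appears, so each such result is informative about a named potential risk. If the laboratory tables can say only high or not high, they lose the size of the rise. In one situation they lose the rise altogether.

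The BUN and creatinine differences raise a traceability question. A grade assigned during the trial under Protocol Attachment 1 may not match the grade in the final tables, and the SAP does not tell the reader so.

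**Working it through.** No power or sample-size figure is involved, so the check compares the two tables.

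**1. Troponin I under the SAP rules.** Inputs are the protocol footnote, the SAP 7.2 fallback and the SAP 7.2.1 worse-than-baseline rule. The xULN values are illustrative.

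| Screening | Post-boost | Class under SAP | Counted as following vaccination? | Class with protocol steps |
|---|---|---|---|---|
| ≤ULN | 1.1xULN | high | yes | step 1 |
| ≤ULN | 6xULN | high | yes | step 3 |
| 1.1xULN | 6xULN | high at both | no, not worse than baseline | step 1 to step 3, counted |
| missing | 6xULN | high | yes | step 3 |

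Rows 1 and 2 fall in the same category under the SAP. Row 3 drops out of the table. It is a possible case, because inclusion criterion 4.1 admits a subject with an out-of-range screening result that the investigator judges not clinically significant. All rows assume that the unscheduled result is entered in the clinical laboratory data.

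**2. BUN and creatinine cut-offs in SI units.**

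| Test | Document | Grade 1 | Grade 2 | Grade 3 |
|---|---|---|---|---|
| BUN, mmol/L | Protocol | 8.3-9.4 | 9.5-11.2 | >11.2 |
| BUN, mmol/L | SAP | 8.2-9.3 | 9.4-11.1 | >11.1 |
| Creatinine, µmol/L | Protocol | 133-151 | 152-177 | >177 |
| Creatinine, µmol/L | SAP | 133-150 | 151-177 | >177 |

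Every BUN value from 7.5 to 12.9 in steps of 0.1, and every creatinine value from 120 to 199 in steps of 1, was graded under both tables. The disagreements (protocol grade, then SAP grade) are:

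- BUN 8.2: 0, 1
- BUN 9.4: 1, 2
- BUN 11.2: 2, 3
- Creatinine 151: 1, 2

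All other values agree. Creatinine Grade 3 is the same in both tables.

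**3. Which SI bounds follow from the shared mg/dL bounds.** The conversion factors are assumptions from molecular masses: 10/28.014 mmol/L per mg/dL for urea nitrogen, and 10,000/113.12 µmol/L per mg/dL for creatinine.

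- BUN: 23 × 10/28.014 = 8.21; 26 × 10/28.014 = 9.28; 31 × 10/28.014 = 11.07 mmol/L. These round to 8.2, 9.3 and 11.1, the SAP values.
- Creatinine: 1.7 × 10,000/113.12 = 150.3 µmol/L, which rounds to the SAP's 150.

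**4. Rough size of the BUN Grade 3 shift.** The documents give no urea distribution. Assume log-normal values reported to 0.1 mmol/L, with mean (SD) from 4.8 (1.2) to 5.5 (1.5). The Grade 3 difference is P(≥11.15) − P(≥11.25):

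- Mean 4.8, SD 1.2: 0.0195% − 0.0170% = about 0.003 percentage points per draw.
- Mean 5.5, SD 1.5: 0.2783% − 0.2511% = about 0.027 percentage points per draw.

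SAP 1.4 gives about 423 subjects. The Time and Events Schedule gives at most three chemistry draws after the prime: 7 days post-prime, pre-boost and 7 days post-boost. That is 423 × 3 = 1,269 draws, or roughly 0.03 to 0.35 extra Grade 3 results.

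**The case against.** The SAP is not ambiguous: it names Attachment 3, and its fallback tells the programmer what to do with an ungraded test. That stands. The defect is an undeclared departure from the protocol table, not an undefined analysis.

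It can also be said that the SAP follows the FDA scale, of which the sponsor's troponin steps are not a part. This carries less weight. SAP Attachment 3 states that the FDA table has no INR grades, yet it grades INR from another source.

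The protocol footnote does not label its steps Grades 1 to 3. That also stands. Three ordered steps on a three-grade scale suggest it, but the sponsor must confirm it.

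Two stronger readings are tempting, and the documents do not support either.

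- **A reader might infer that Grade 3 laboratory counts depend generally on which table is used.** Creatinine cannot change a Grade 3 count. BUN can do so only at 11.2 mmol/L, and only if results are graded in SI units; the documents reviewed do not state the reporting unit.
- **A reader might infer that a severe troponin rise would vanish from safety reporting.** A subject who was normal at screening is still tabulated as above normal and appears in the SAP 7.2.3 listing. Clinically relevant rises are recorded and analysed as adverse events (SAP 7.2), with listings and, for some categories, narratives (SAP 7.1.3). One gap remains: that listing covers findings following vaccination. If the phrase carries its 7.2.1 meaning, a subject already above ULN at screening would be missing there too, which leaves the adverse event route.

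Finally, safety is descriptive ("No formal statistical testing of safety data is planned"), so no test result depends on these cut-offs.

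**Conclusion.** The point holds in limited form. SAP Attachment 3 omits the protocol's three troponin I steps, and SAP Section 3 does not say so. As written, a post-boost rise of 5xULN or more cannot reach the top severity category, and a rise in a subject already above ULN at screening is not counted as a post-vaccination abnormality. This rests on the unscheduled result being in the laboratory data and on the footnote's steps being meant as severity grades.

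The BUN and creatinine differences are real but minor. Four reported values are affected, and one of them (BUN 11.2 mmol/L) touches Grade 3. The expected change is below one Grade 3 result in the whole study under the assumed urea distributions. The rule that values within laboratory normal limits are not graded would remove the Grade 1 difference at 8.2 entirely if the upper limit is 8.2 mmol/L or higher.

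Overall impact is small. The documents give no expected number of troponin tests, but few are likely because testing is symptom-driven. The case for acting rests on troponin. Part of Protocol Attachment 1 was not available for review, so the comparison covers the visible chemistry, hematology and coagulation entries only.

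**What to change.** 1. Add the protocol's three troponin I steps to SAP Attachment 3 as ordered grades, with the sponsor confirming that they correspond to Grades 1 to 3. The worst-grade and worse-than-baseline rules in 7.2.1 and the tables in 7.2.3 then apply to unscheduled results.
2. Reconcile the BUN and creatinine SI cut-offs between the two attachments. The analysis can keep the SAP bounds, since they follow from the shared mg/dL bounds. Align the creatinine direction label as well, which is N (not graded) in the protocol and HI in the SAP.
3. Declare the differences in SAP Section 3, and list any result whose grade differs under Protocol Attachment 1.

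This concerns the grading used in the analysis only, not any decision about vaccination or subject care.

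The cost is one table row, a short statement and a short listing in a SAP amendment before database lock. No new data are needed. A few tabulated grades may still differ from those applied at the sites, and the listing would show them.
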